### **3.4. Stopping Rules for Individual Subjects**

Subjects who meet any of the following criteria should be discontinued from the study and complete an Early Termination Visit and return for Post-treatment Follow-up visits:

- Elevation of ALT and/or AST that is greater than the ULN and  $> 5x$  baseline or nadir confirmed by immediate repeat testing unless laboratory results are assessed by both the investigator and Gilead Medical Monitor as having an explanation other than drug induced liver injury and it is deemed in the best interest of the subject to continue HCV treatment
- Confirmed elevation of ALT  $>15 x$  ULN (unrelated to any interventional procedures)
- Confirmed total bilirubin  $>10 x$  ULN (unrelated to any interventional procedures)
- Confirmed total bilirubin  $>3x$  baseline or  $3x$  nadir (unrelated to any interventional procedures)
- Any Grade 3 or greater rash associated with constitutional symptoms
- Any non-laboratory Grade 4 events assessed as related to administration of SOF/VEL
- Worsening of disease state as evidenced by progressing hepatic decompensation and/or progression of Child-Pugh Score (CPT) to  $\geq 10$
- Steroid-resistant acute allograft rejection

The Gilead Medical Monitor should be consulted prior to discontinuation of SOF/VEL unless the investigator believes that immediate action is warranted to ensure the continued safety of the subject.

Any questions regarding toxicity management should be directed to Gilead Medical Monitor.

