### **3.5. Discontinuations**

If the subject meets the Virologic Response-Based Criteria (Section 3.3), they should complete an Early Termination Visit as soon as possible after SOF/VEL is discontinued and complete post-treatment visits up to 30 days after the last dose of SOF/VEL to assess for safety.

If the subject meets the Stopping Rules for Individual Subjects (Section 3.4) or other criteria for discontinuation of study treatment (Section 3.7), prior to completion of SOF/VEL dosing period, the subject should complete an Early Termination Visit as soon as possible after SOF/VEL is discontinued and complete the post-treatment assessments as described in Section 6.3 and in Study Procedures Appendix 2.

Subjects discontinuing treatment prior to completion of dosing period for reasons other than those described in Sections 3.3, 3.4 and 3.7 should complete an Early Termination Visit as soon as possible after SOF/VEL is discontinued. The subject should also complete the post-treatment assessments as described in Section 6.3 and in Study Procedures Appendix 2.

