#### **6.2.2. Week 2 ( $\pm$ 3 days)**

The following procedures/assessments are to be completed at the end of Week 2:

- Obtain vital signs (resting blood pressure, pulse, respiratory rate and temperature)
- Assessment of AEs and concomitant medications
- Obtain blood samples for:
  - Hematology
  - Chemistry
  - HCV RNA
  - Viral sequencing
  - PK sample
- Assess adherence with study drug dosing regimen including pill count

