### **6.2.3. Weeks 4 and 8 ( $\pm$ 3 days)**

The following procedures/assessments are to be completed at the end of Weeks 4 and 8:

- Obtain vital signs (resting blood pressure, pulse, respiratory rate and temperature)
- Assessment of AEs and concomitant medications
- Conduct pregnancy prevention counseling
- Obtain blood samples for:
  - Hematology
  - Chemistry
  - HCV RNA
  - Viral sequencing
  - PK sample
- Obtain urine sample for pregnancy test (for females of child bearing potential only)
- Assess adherence with study drug dosing regimen including pill count
- Dispense study drugs as directed by the IWRS

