## **6.6. Procedures and Specifications**

### **6.6.1. Clinical Laboratory Analytes**

Hematology: Hematocrit, Hemoglobin (Hb), Platelet count, Red blood cell count (RBC), White blood cell count (WBC) with differential (absolute and percentage) including Lymphocytes, Monocytes, Neutrophils, Eosinophils, Basophils, Reticulocyte count and mean cellular volume (MCV).

Coagulation: INR, Prothrombin time (PT), Activated partial thromboplastin time (APTT).

Chemistry: Alanine aminotransferase (ALT/SGPT), Aspartate aminotransferase (AST/SGOT), Albumin, Alkaline phosphatase, Bicarbonate, Creatinine, Creatine kinase (CK), Total Bilirubin (reflex to Direct Bilirubin), Glucose, Lipase, Potassium, Phosphate, Sodium, Uric Acid; FibroTest®/APRI calculation, and Direct Bilirubin at Screening only.

Virological Tests: Serologies for HCV and HBV, Serology and/or antigen testing for HIV including reflex testing, as necessary, HCV RNA will be measured using the COBAS® Ampliprep/COBAS® TaqMan® HCV Quantitative Test, v2.0. HCV genotype and subtype will be determined using the Siemens VERSANT® HCV genotype INNO-LiPA 2.0 Assay. The Abbott RealTime HCV genotype II assay is unable to result HCV genotype 6; these subjects will be identified as "Unable to genotype" on the laboratory report as well as those with mixed genotype will be considered indeterminate. Gilead reserves the right to use alternate assays for HCV RNA, and HCV genotype should the above assays become unavailable or the results are indeterminate.

IL28B genotype will be determined by polymerase chain reaction (PCR) amplification of the SNP, rs12979860, with sequence specific forward and reverse primers and allele specific fluorescently labeled TaqMan® MGB probes. Gilead reserves the rights to use an alternate assay for IL28B determination should the above assay become unavailable.

Pregnancy Tests: Serum  $\beta$ -hCG or Urine  $\beta$ -hCG (if positive, requires immediate confirmation with Serum  $\beta$ -hCG).

Additional Tests: Urine Drug screen (for Amphetamines, Cocaine, Methadone, Opiates) and Hemoglobin A1c (HbA1c)

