#### **6.6.6. Child-Pugh Score**

Child-Pugh score should be assessed at Screening, Week 12, post-treatment Week 4 and post-treatment Week 12. Please refer to [Appendix 4](#) for more information regarding the Child-Pugh classification.

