**Appendix 2. Study Procedures Table**

	Screen	Baseline/Day 1 b	On-treatment Week				Post-treatment Week	
			2	4	8	12/ET	4	12
Clinical Assessments								
Informed Consent	X							
Determine Eligibility	X	X						
Medical History	X							
Physical Examination	X	X				X	X	X
Height	X							
Weight	X	X				X		
Vital Signs	X	X	X	X	X	X	X	X
12-Lead ECG	X							
CPT score	X					X	X	X
Adverse Events and Concomitant Medications	X	X	X	X	X	X	X	X
Pregnancy Prevention Counseling		X		X	X	X	X	
Review of Study Medication Compliance			X	X	X	X		
Study Drug Dispensing a		X		X	X			
Laboratory Assessments								
Hematology, Chemistry g	X	X	X	X	X	X	X	X
Coagulation Tests	X	X				X		
Urinalysis	X	X				X		
HCV RNA c	X	X	X	X	X	X	X	X f

	Screen	Baseline/Day 1 b	On-treatment Week				Post-treatment Week	
			2	4	8	12/ET	4	12
Viral Sequencing c		X	X	X	X	X	X	X f
Single PK			X	X	X	X		
Serum $\beta$ -hCG or Urine Pregnancy Test d	X	X		X	X	X	X	
Urine Drug Screen	X							
HCV Genotyping, IL28B	X							
HCV, HIV, HBV Serology	X							
HbA1c, Fibrotest ®	X							
Archive Sample e		X				X		
Pharmacogenomic Sample e		X						

a The IWRS will provide direction on the specifics of each subject's study drug dispensing

b Baseline/Day 1 assessments must be performed prior to dosing

c Viral sequencing samples for virologic sequencing required at baseline and after any visit where a previously undetectable HCV RNA becomes detectable

d Serum  $\beta$ -hCG pregnancy test performed at screening and for confirmation of positive urine pregnancy test.

e Only for subjects who have provided consent for this sample and testing.

f Only for subjects with HCV RNA  $\geq$ LLOQ at post-treatment week 12 visit will be asked to return after for a confirmatory visit where additional samples are collected.

g CrCl will be calculated at all visits where a blood sample is drawn

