3.8.2. Analysis Windows

Subject visits might not occur on protocol-specified days. Therefore, for the purpose of analysis, observations will be assigned to analysis windows.

In general, the baseline value will be the last nonmissing value on or prior to the first dose date of study drug.

HCV RNA, vital signs, and safety laboratory data collected up to the last dose date + 3 days are considered to be on-treatment data and HCV RNA, vital signs, and safety laboratory data collected after the last dose date + 3 days are considered posttreatment data. The analysis windows for on-treatment HCV RNA, vital signs and safety laboratory data are provided in [Table 3-1](#).

Table 3-1. Analysis Windows for On-treatment HCV RNA, Vital Signs and Safety Laboratory Data

Nominal Visit	(SOF/VEL 12 Weeks)		
	Nominal Day	Lower Limit	Upper Limit
Baseline ^a	1	(none)	1
Week 2	14	2	21
Week 4	28	22	42
Week 8	56	43	70
Week 12 ^a	84	71	≥ 85

a Coagulation and urinalysis tests will only be collected at baseline and Week 12.

HCV RNA, vital sign, and safety laboratory data collected after the last dose date + 3 days will be assigned to a posttreatment follow-up (FU) visit. Visit windows will be calculated from the last dose date (ie, FU Day = collection date minus the last dose date) as shown in [Table 3-2](#).

Table 3-2. Analysis Windows for Posttreatment HCV RNA, Vital Signs and Hematology/Chemistry Safety Laboratory Data

Nominal FU ^a Visit	HCV RNA			Vital Signs and Safety Laboratory Data ^b		
	Nominal FU Day	Lower Limit	Upper Limit	Nominal FU Day	Lower Limit	Upper Limit
FU-4	28	21	69	28	4	30
FU-12	84	70	146		NA	

a FU-x visit = posttreatment Week-x follow-up visit.

b Vital signs and hematology/chemistry safety labs will only be summarized for the FU-4 visit (up to 30 days after last dose). Coagulation and urinalysis tests are not collected at posttreatment visits.

ECG data collected at the screening visit will be listed using the nominal visit.

3.8.3. Selection of Data in the Event of Multiple Records in an Analysis Window

Depending on the statistical analysis method, single values may be required for each analysis window. For example, change from baseline by visit usually requires a single value, whereas a time-to-event analysis would not require 1 value per analysis window.

If multiple valid nonmissing numeric observations exist in an analysis window, records will be chosen based on the following rules if a single value is needed:

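### CPT of 10 or more requires stopping, but no CPT or PT/INR is scheduled on treatment before Week 12/ET, so a narrow laboratory-driven route to 10 rests on discretionary testing

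*Protocol*

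**What the plan says.** Protocol Section 3.4 lists among its individual stopping rules "Worsening of disease state as evidenced by progressing hepatic decompensation and/or progression of Child-Pugh Score (CPT) to" 10 or more. The wording joins the two limbs with and/or, so either is sufficient.

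Section 6.6.6 fixes when the score is taken: "Child-Pugh score should be assessed at Screening, Week 12, post-treatment Week 4 and post-treatment Week 12". The visit lists in Sections 6.2.2 (Week 2) and 6.2.3 (Weeks 4 and 8) contain chemistry and AE assessment but no coagulation test and no CPT; the Appendix 2 table agrees. The Day 1 coagulation draw cannot serve as an on-treatment value, because "Baseline/Day 1 assessments must be performed prior to dosing". The SAP describes the same schedule in the footnote to Table 3-1: "Coagulation and urinalysis tests will only be collected at baseline and Week 12".

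An early termination visit comes after the decision to stop: under Section 3.5 the subject should "complete an Early Termination Visit as soon as possible after SOF/VEL is discontinued".

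Appendix 4 scores encephalopathy, ascites, bilirubin, albumin and PT/INR at 1 to 3 points each and adds them. Section 6.6.1 lists bilirubin and albumin under chemistry and INR under a separate coagulation panel. Section 4.3 excludes a screening CPT above 7.

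**The concern.** A mandatory stopping criterion should be assessable from required data while the subject is still taking the drug. Here one of the five inputs to the score is not collected at any required visit between the first dose and Week 12/ET, and the score itself is not calculated there either. A subject whose bilirubin, albumin and clotting deteriorate together, without ascites or encephalopathy, could reach the threshold without any required procedure showing it. At stake is timely stopping in a small number of transplant recipients whose graft function is worsening. The efficacy estimate is not at stake.

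**Working it through.** The plan gives no figure of its own on this point, so the check compares the schedule with the scoring table.

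**1. Schedule (Protocol Sections 6.1 and 6.2, Appendix 2).**

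| | Screening | Day 1 | Wk 2 | Wk 4 | Wk 8 | Wk 12/ET |
|---|---|---|---|---|---|---|
| CPT | yes | no | no | no | no | yes |
| PT/INR | yes | pre-dose | no | no | no | yes |
| Bilirubin, albumin | yes | yes | yes | yes | yes | yes |
| Physical examination | yes | yes | no | no | no | yes |
| AE assessment | yes | yes | yes | yes | yes | yes |

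On the nominal days in SAP Table 3-1, scheduled PT/INR results are 84 − 1 = 83 days apart. The longest chemistry gap is 28 days.

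**2. How much of the rule needs INR.** There are 3^5 = 243 combinations. Let S be the sum of the four components other than INR. The number of ways to obtain S = 7, 8, 9, 10, 11, 12 is 16, 19, 16, 10, 4, 1.

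- S of 9 or more reaches 10 whatever the INR: (16 + 10 + 4 + 1) × 3 = 93.
- S = 8 needs INR scored 2 or 3: 19 × 2 = 38.
- S = 7 needs INR scored 3: 16 × 1 = 16.
- S of 6 or less cannot reach 10: 6 + 3 = 9.

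Total at 10 or more: 93 + 38 + 16 = 147, of which 54 need INR and 93 (63%) do not.

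**3. Which of the 54 are left uncovered.**

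- *No ascites, no encephalopathy: 4.* The maximum without INR points is 1 + 1 + 3 + 3 + 1 = 9. The four (bilirubin, albumin, INR) patterns are 2,3,3; 3,2,3; 3,3,2; 3,3,3. They are the only laboratory-only patterns, and 4/147 = 2.7%.
- *Mild or moderate ascites, no encephalopathy: 7.* With ascites at 2 points, 10 combinations reach 10; 3 have bilirubin and albumin both at 3 and need no INR, and the other 7 need it. These matter only if the ascites was present and controlled at entry. New ascites would generally engage the clinical limb.
- *Encephalopathy or severe ascites: 54 − 4 − 7 = 43.* Section 4.3 excludes uncontrolled ascites and hepatic encephalopathy at entry, so these findings would be new and would generally engage the clinical limb.

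**4. Overlap with the rule on bilirubin above 3 times baseline or nadir.** The baseline or nadir values below are assumptions.

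| Baseline/nadir (mg/dL) | Rule fires above | Uncovered in the 2-point band (2–3) | Uncovered in the 3-point band (above 3) |
|---|---|---|---|
| 0.67 | 2.0 | essentially none | none |
| 1.0 | 3.0 | all | none |
| 1.2 | 3.6 | all | 3.0–3.6 |
| 1.5 | 4.5 | all | 3.0–4.5 |
| 2.0 | 6.0 | all | 3.0–6.0 |

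Three of the four laboratory-only patterns need bilirubin above 3 mg/dL. Once confirmed, that is caught if baseline or nadir is 1.0 or lower. The fourth needs bilirubin of 2 to 3 mg/dL, and that whole band is covered only below about 2.0/3 = 0.67 mg/dL.

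**5. An example.** A screening score of 1 + 1 + 3 + 1 + 1 = 7, with bilirubin already above 3 mg/dL, satisfies the CPT limit. If albumin falls below 2.8 g/dL and INR reaches 1.7 with bilirubin unchanged, the score is 1 + 1 + 3 + 3 + 2 = 10. The rule on change in bilirubin does not fire, and no required test shows the INR.

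**The case against.** The strongest reply is that an unscheduled test is still an available test. A reader might infer that the plan cannot evaluate its CPT criterion on treatment. The documents do not support that: 93 of 147 combinations need no INR points, the clinical limb belongs to the same criterion, and Section 6.2.5 allows an unscheduled visit with tests at the investigator's discretion. Section 3.7 (investigator judgment) and Section 9.1.6 (central monitoring of safety data) add further safeguards. All of this stands and limits the point, but none of these provisions requires an INR or a CPT.

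A second reply is that event-driven testing is normal among stopping rules: steroid-resistant rejection rests on biopsy, and no on-treatment biopsy is scheduled. That is fair. However, Section 5.5 says when presumptive rejection should be confirmed by biopsy, whereas no equivalent prompt exists for INR.

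A third reply is that chemistry already gives the warning. It does: all four laboratory-only patterns have bilirubin of at least 2 mg/dL and albumin of 3.5 g/dL or less, with at least one of the two at 3 points. The plan leaves the response to that warning to discretion, and the change proposed here only makes the response explicit.

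Two further inferences should be resisted. Subjects carrying encephalopathy in from entry might be added to the gap, but on a plain reading exclusion criterion 8 in Section 4.3 keeps them out. The 9.6% with a CPT increase in the CPT class B study (22 of 229, Section 1.2.2.1.4) might be scaled to 80 subjects. That figure covers a rise of any size to post-treatment Week 12, in decompensated patients, pooled over 12- and 24-week arms including one with ribavirin. Its denominator matches the 229 SVR12 achievers in the same section's MELD result, not the 267 treated. It supports neither a subject count nor a test count.

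**Conclusion.** The point holds as a narrow gap and a cheap improvement. Followed as written, the schedule leaves part of a mandatory stopping rule to discretion throughout dosing. The exposed part is the 4 laboratory-only combinations, when baseline or nadir bilirubin is above about 0.67 mg/dL (2-point bilirubin) or 1.0 mg/dL (3-point bilirubin), and arguably the 7 of 10 combinations open to a subject entering with controlled ascites.

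These are counts of score patterns and carry no probabilities. Few subjects are expected, because entry CPT of at most 7 means a rise of at least 10 − 7 = 3 points, but no expected number can be derived from the documents. The conclusion assumes that new ascites or encephalopathy would be recognised through AE assessment, since the visit schedule has no physical examination at Weeks 2, 4 or 8. The SVR12 analysis is unaffected.

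**What to change.** Add one sentence to Protocol Sections 6.2.2 and 6.2.3, with matching entries in 6.6.6 and Appendix 2:

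*At Weeks 2, 4 and 8, if the CPT components other than PT/INR total 7 or more, or an AE suggests hepatic decompensation, obtain PT/INR and calculate CPT promptly.*

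Below 7 the score cannot reach 10 (6 + 3 = 9), so the trigger misses no route at those visits. Keep the threshold of 10. Routine INR for all subjects with cirrhosis is not needed.

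The cost is a protocol amendment and a small number of extra INR tests, which the documents do not allow to be estimated. The ceiling at the scheduled visits is 80 × 3 = 240. No scheduled visit is added. If chemistry results arrive after the subject has left, the INR may need a return draw, for which Section 6.2.5 already provides.

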### **3.5. Discontinuations**

If the subject meets the Virologic Response-Based Criteria (Section 3.3), they should complete an Early Termination Visit as soon as possible after SOF/VEL is discontinued and complete post-treatment visits up to 30 days after the last dose of SOF/VEL to assess for safety.

If the subject meets the Stopping Rules for Individual Subjects (Section 3.4) or other criteria for discontinuation of study treatment (Section 3.7), prior to completion of SOF/VEL dosing period, the subject should complete an Early Termination Visit as soon as possible after SOF/VEL is discontinued and complete the post-treatment assessments as described in Section 6.3 and in Study Procedures Appendix 2.

Subjects discontinuing treatment prior to completion of dosing period for reasons other than those described in Sections 3.3, 3.4 and 3.7 should complete an Early Termination Visit as soon as possible after SOF/VEL is discontinued. The subject should also complete the post-treatment assessments as described in Section 6.3 and in Study Procedures Appendix 2.

### **3.6. Assessments for Premature Discontinuation from Study**

If a subject discontinues SOF/VEL dosing (for example, as a result of an adverse event [AE]), every attempt should be made to keep the subject in the study and continue to perform the required study-related post-treatment assessments and procedures (see Section 6.3). If this is not possible or acceptable to the subject or investigator, the subject may be withdrawn from the study.

### **3.7. Criteria for Discontinuation of Study Treatment**

When medically feasible, the Medical Monitor must be consulted prior to subject discontinuation.

Study drug must be discontinued in the following instances:

- Intercurrent illness that would, in the judgment of the investigator, affect assessments of clinical status to a significant degree
- Unacceptable toxicity, as defined in the toxicity management section of the protocol (Section 7.5), or toxicity that, in the judgment of the investigator, compromises the ability to continue study-specific procedures or is considered to not be in the subject's best interest
- Subject requests to discontinue for any reason; it is important to determine whether the withdrawal of consent is primarily due to an AE, lack of efficacy or other reason
- Subject non-compliance
- Pregnancy
- Discontinuation of the study at the request of Gilead, regulatory agency or an IRB/IEC

**3.8. Biomarker Testing**

**3.8.1. Biomarker Samples for Optional Future Research**

PPD [Redacted]

[Redacted]

[Redacted]

[Redacted]

[Redacted]

[Redacted]

**3.8.2. Biomarker Samples for Optional Pharmacogenomics Research**

PPD [Redacted]

PPD  
[Redacted text block]

[Redacted text block]

[Redacted text block]

[Redacted text block]

[Redacted text block]

## **4. SUBJECT POPULATION**

### **4.1. Number of Subjects and Subject Selection**

Approximately 80 chronic HCV infected subjects who had a liver transplant will be enrolled in this study. Patients both with cirrhosis (if compensated) and without cirrhosis and with treatment experienced (if non-NS5A) or treatment naïve will be eligible.

In order to manage the total study enrollment, Gilead Sciences, Inc., at its discretion, may suspend screening and/or enrollment at any site or study-wide at any time.

### **4.2. Inclusion Criteria**

Subjects must meet all of the following inclusion criteria to be eligible for participation in this study:

- 1) Willing and able to provide written informed consent
- 2) Males and females, age  $\geq 18$  years old
- 3) Chronic HCV infection ( $\geq 6$  months) documented pretransplantation by prior medical history or liver biopsy
- 4) HCV RNA  $\geq 10^4$  IU/mL at screening
- 5) No clinical signs of rejection for 3 months prior to the Screening visit
- 6) Primary or secondary (re-transplant), liver alone or liver and kidney transplant recipient from deceased or living donor (regardless of the HCV status of the liver donor)
- 7) Liver transplant  $\geq 3$  months prior to screening
- 8) A body mass index (BMI) of  $\geq 18$  kg/m^2
- 9) Subjects must have a determination of treatment experience (treatment naïve v. treatment experienced). Treatment naïve is defined as having never been exposed to an approved or experimental HCV-specific direct acting antiviral agents or prior treatment of HCV with interferon or ribavirin. All other patients will be considered treatment experienced
  - a) If treatment experienced, the subject's medical records must include details of prior treatment regimen(s). Any prior use of SOF or other nucleotide analogue HCV NS5B inhibitor should be documented. Previous use of an NS5A inhibitor is not allowed.

10) Subjects must have appropriate testing for determination of cirrhosis status.

- a) Presence of cirrhosis is defined as any one of the following:
  - i) Fibrotest® score > 0.75 AND an AST platelet ration index (APRI) > 2 performed during Screening
  - ii) Fibroscan with a result of > 12.5 kPa within ≤ 6 months of Baseline/Day 1
  - iii) Liver biopsy showing cirrhosis (e.g., Metavir score = 4 or Ishak score ≥ 5)
- b) Absence of cirrhosis is defined as any one of the following:
  - i) Fibrotest score ≤ 0.48 AND APRI ≤ 1 performed during Screening
  - ii) Fibroscan with a result of ≤ 12.5 kPa within ≤ 6 months of Baseline/Day 1
  - iii) Liver biopsy performed within 2 years of Screening showing absence of cirrhosis

In the absence of a definitive diagnosis of presence or absence of cirrhosis by Fibrotest /APRI using the above criteria, a liver biopsy or fibroscan is required. A diagnosis of cirrhosis will supersede a diagnosis of non-cirrhosis and be considered definitive.

- 11) Liver imaging within 6 months of Baseline/Day 1 is required in cirrhotic subjects only to exclude hepatocellular carcinoma (HCC)
- 12) A negative serum pregnancy test is required for female subjects (unless permanently sterile or greater than two years post-menopausal)
- 13) Male subjects and female subjects of childbearing potential who engage in heterosexual intercourse must agree to use protocol specified method(s) of contraception as described in [Appendix 6](#)
- 14) Lactating females must agree to discontinue nursing before the study drug is administered
- 15) Subject must be able to comply with the dosing instructions for study drug administration and able to complete the study schedule of assessments

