This is a multicenter, open-label, Phase 2 study designed to evaluate SOF/VEL for 12 weeks in post liver transplant subjects with recurrent chronic HCV infection. Approximately 80 subjects with chronic HCV will be enrolled. Approximately 20% will have genotype 3 HCV infection and up to approximately 20% with Metavir stage 3 or 4 fibrosis/cirrhosis or corresponding fibrosis degree is approximately 20% at baseline will be enrolled.

This study will evaluate the safety and efficacy of SOF/VEL FDC for 12 weeks in subjects with recurring HCV infection (without cirrhosis or with compensated liver cirrhosis) following a liver transplant.

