## 5.5. Management of Rejection

The diagnosis of ACR, based on liver biopsy, and the decision to treat are important concerns due to the potential interactions between immunosuppression and the success of HCV treatment. It is expected that this will not be a common occurrence in this study, given that subjects must be stable and at least 6 months from transplant at study entry. Sites will be asked to follow their institutional guidelines for the management of organ rejection, but to also give consideration to the following issues as related to this study protocol. (This information is provided for guidance and consistency across subjects, but variations will not be considered protocol violations if the treatment is consistent with the guidelines of the institution).

- It is important to use standard criteria for diagnosis of rejection, to avoid over-treatment of milder grades of rejection with corticosteroids whenever possible, and to standardize the exposure to corticosteroids when treatment for rejection is necessary
- Episodes of rejection will be recorded on the CRF and severity will be graded (grading by Banff criteria, [Appendix 5](#))
- It is preferred that mild ACR is to be treated with upward adjustment of maintenance immunosuppression rather than the addition of corticosteroids
- Cases of moderate or severe ACR may require treatment with corticosteroids
- Cases of presumptive rejection should be confirmed by liver biopsy (as per standard practice) if more than one dose of corticosteroid is required
- Subjects with steroid-resistant ACR should be discontinued from the study so that management of their organ rejection can be the primary focus of treatment.

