### 6.1. Screening Assessments

#### 6.1.1. Screening Visit (Day 28 to Day 0)

Subjects will be screened within 28 days of Baseline/Day 1 visit. The screening window can be extended to 42 days for subjects requiring liver biopsy, additional HCV genotype testing or for extenuating circumstances.

The following will be performed and documented:

- Obtain written informed consent

PPD

- Determine inclusion and exclusion eligibility
- Obtain medical history, including
  - Hepatitis C history
  - Liver transplant history
  - Liver biopsy results (if applicable)

- Determine cirrhosis status as defined in Section 4.1
  - If the presence of cirrhosis is determined, then appropriate diagnostic imaging (CT or Ultrasound) should be performed or confirmed to have been performed within 6 months of screening to exclude the presence of hepatocellular carcinoma (HCC)
- Determine treatment experience status as defined in Section 4.1
  - If treatment experienced, record the duration(s) and type(s) of the prior treatment administered.
  - If treatment experienced, record whether or not any past treatment regimens contained SOF or other nucleotide analogue HCV NS5B inhibitors.
- Complete physical examination including, vital signs (temperature, blood pressure, pulse, respiratory rate), body weight, and height
- Obtain details of concomitant medications
- Perform 12-lead ECG
- Fibrosis Assessment
- Calculate CPT score
- Obtain blood samples for tests as listed in Section 6.6.2:
  - Hematology
  - Chemistry
  - Coagulation tests
  - HCV RNA
  - Determination of HCV viral genotype and subtype
  - HCV antibody, HIV, and HBV surface antigen (HBV serology)
  - HbA1c
  - IL28B
  - Serum  $\beta$ -hCG pregnancy test for females of childbearing potential only

- Obtain urine sample for:
  - Urinalysis
  - Serum pregnancy test for females of childbearing potential
  - Urine drug screen
- Record any serious adverse events and all adverse events related to protocol mandated procedures occurring after signing of the consent form.
- Retests of Screening labs are permitted only if there is reason to believe the retest value will be within accepted parameters, for example, if the initial exclusionary value was either due to a sample processing error or due to an extenuating circumstance such as intercurrent illness.

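### Could a biopsy of a removed liver label a subject with a non-cirrhotic graft as cirrhotic?

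*Protocol*

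**What the plan says.** Protocol Section 4.2, criterion 10, defines cirrhosis as present if any one of three routes is met. The FibroTest/APRI route must be carried out during Screening, and the Fibroscan route within 6 months of Day 1. The biopsy route, "Liver biopsy showing cirrhosis (e.g., Metavir score = 4 or Ishak score" of 5 or more, carries no date and names no organ. The matching route to absence of cirrhosis is "Liver biopsy performed within 2 years of Screening showing absence of cirrhosis", which also names no organ. If results conflict, "A diagnosis of cirrhosis will supersede a diagnosis of non-cirrhosis and be considered definitive".

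Criterion 6 of the same section admits a "Primary or secondary (re-transplant), liver alone or liver and kidney transplant recipient from deceased or living donor", so some subjects may have lost an earlier graft as well as the native liver. Criterion 3 requires chronic HCV infection "documented pretransplantation by prior medical history or liver biopsy". Section 6.1.1 collects "Liver biopsy results (if applicable" as part of the medical history.

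The label is then used in SAP Section 3.4 (SVR12 by cirrhosis, and by treatment experience crossed with cirrhosis), SAP Section 6.1.4 (point estimate and exact interval for each subgroup), SAP Section 5.2 (baseline table and listings) and criterion 11 (HCC imaging for cirrhotic subjects).

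**The concern.** Three features combine: any one route suffices, the biopsy route is undated and does not name the organ, and a positive diagnosis wins every conflict. Read word for word, a biopsy of a removed cirrhotic liver would outrank a current Fibroscan of 12.5 kPa or less. This is not far-fetched here. Section 1.1 describes HCV as a leading cause of cirrhosis and a primary reason for transplantation, and criterion 3 expects pre-transplant biopsy reports in some records.

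At stake would be the cirrhosis subgroup. Subjects with non-cirrhotic grafts would pull its SVR12 towards the non-cirrhotic rate. They would also enlarge the group, so its exact interval would look more precise than the data on cirrhotic grafts justify. A wrong positive label would add HCC imaging, not remove it.

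**Working it through.** **Which liver is meant?** The relevant texts, side by side:

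- Criterion 10 opens by asking for suitable testing to establish each subject's cirrhosis status. Histology of an organ no longer in the body does not establish that.
- The sentence just before the override rule says that when FibroTest/APRI is inconclusive, either a biopsy or a Fibroscan must be done. The two are interchangeable there, and a Fibroscan can only measure the liver in place.
- Sections 3.1, 3.2 and 6.1.1 lengthen screening to 42 days for subjects who need a biopsy, so the biopsy in view is mainly one taken at study entry.
- When the protocol means the period before transplant it says so, as in criterion 3: "documented pretransplantation by prior medical history or liver biopsy". Where histology is unqualified it concerns the graft. Section 5.5 has "The diagnosis of ACR, based on liver biopsy, and the decision to treat are important concerns", and exclusion criterion 6 concerns unresolved rejection.
- Section 1.3 describes the population as having "recurring HCV infection (without cirrhosis or with compensated liver cirrhosis) following a liver transplant" and sets the Metavir 3 or 4 target at baseline. Counting removed livers would make that target of about 20%, and the non-cirrhotic part of the population, hard to interpret.
- In Section 6.1.1 the biopsy history, the determination of cirrhosis status and the fibrosis assessment are separate entries. Nothing says that the history entry feeds the label.

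**Does it touch the primary result?** The plan's one precision figure is an exact 95% interval at most 23% long with 80 subjects. Maximising the Clopper-Pearson length over all outcomes gives the widest interval at 40 of 80: 38.6% to 61.4%, a length of 22.8%. The figure reproduces. Neither it nor the primary SVR12 analysis uses cirrhosis status.

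**How large could the subgroup shift be?** Let m be the mislabelled share of the subjects called cirrhotic, and pN and pC the non-cirrhotic and cirrhotic SVR12 rates. The labelled rate is (1 − m) × pC + m × pN, so the bias is m × (pN − pC).

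- Genotype 3 (Protocol 1.2.2.1.3): pN − pC = 191/197 − 73/80 = 0.9695 − 0.9125 = 0.0570.
- Genotypes 1, 2, 4, 5 and 6 (Protocol 1.2.2.1.1): 19.4% of 624 is about 121 cirrhotic subjects, and 99.2% of 121 is about 120 responders. The remainder is (618 − 120)/(624 − 121) = 498/503. So pN − pC = 0.9901 − 0.9917 = about −0.0017.
- Assuming 20% genotype 3 among cirrhotic subjects: 0.2 × 0.0570 + 0.8 × (−0.0017) = about 0.010, or 1.0 point.

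The bias is therefore about 0.25 points at m = 25%, 0.5 at m = 50%, and 1.0 only at m = 100%. For comparison, the Metavir 3 or 4 target is 0.20 × 80 = 16 subjects, of whom cirrhotic subjects are only a part. Even with all 16 in the subgroup, 15 of 16 responders has an exact interval of 69.8% to 99.8%, about 30 points long.

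**And the false precision?** If all n subjects respond, the exact lower limit is 0.025^(1/n). With an assumed 8 of 8 it is 63.1%. Adding 4 mislabelled responders makes it 12 of 12 and 73.5%. This shows what the distortion would look like if it occurred. The counts are assumed, and nothing in the documents supports them.

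**The case for a change.** The best case for acting is that intent is clear but the operative definition does not state it. The context is strong, yet an earlier biopsy can count under criterion 10, so nothing expressly excludes a removed liver. Nor does any section require the biopsy date to be compared with the transplant date. Section 6.1.1 even sends the reader to Section 4.1 for the definition, which is not there. Readers will also care about cirrhotic grafts: Sections 1.1 and 1.3 describe an existing ribavirin-free option whose duration depends on cirrhosis, whereas Section 1.5 presents SOF/VEL as a single-duration regimen. The interval effect in a small subgroup could exceed the 1-point shift in the estimate, and the remedy would be a short phrase.

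The silence stands, and it applies equally to 10(b)(iii): transplant is allowed from 3 months before screening, so a biopsy within 2 years could predate it. The rest falls short of requiring a change. The same context fixes the meaning of both biopsy routes. SAP Section 5.2 plans a by-subject listing of how cirrhosis was determined and reports time since the latest transplant, so a misplaced biopsy could be noticed. Data queries under Protocol Section 9.1.6 give a further chance, although the eCRF itself is not available to check. Rewording an inclusion criterion is also not free: Sections 9.1.2 and 9.2.1 require ethics approval of protocol modifications.

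**Conclusion.** No change is needed. Criterion 10 leaves out a detail that investigators in a transplant trial would supply correctly from the surrounding text. The overall SVR12, its exact interval and the sample-size statement are unaffected. Any effect would be confined to the baseline table, HCC imaging and exploratory cirrhosis subgroups, which are descriptive; SAP Section 6.1.2 plans no hypothesis test. The frequency of mislabelling cannot be determined from the documents. The ceiling of about 1.0 point rests on non-transplant response rates, the assumed 20% genotype 3 share and every labelled subject being wrong. The interval illustration rests on assumed counts with every subject responding. Neither shows an effect on this trial's results.
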